8.5.5 External Data

External data from published studies or other publicly available sources such as registry databases will be identified. These additional data sources may be utilised to provide supporting data and context, and, if feasible, background event rates for risk assessment analyses (ACCESS 2020).

8.6 Study Size

This study plans to enrol 15,000 participants in at least 4 countries in the EU (Germany, France, Spain, and Sweden). The Sponsor will aim for at least 50% of participants to be 65 years of age or older and approximately equal proportions of male and female participants.

As the COVID-19 pandemic is a dynamic situation, the enrolment target may be amended if recruitment forecasts change.

8.7 Data Management

Data management will be performed by a contract research organisation (CRO) according to the Data Management Plan.

8.7.1 Digital Platform Data

All data entered into the study app or web portal will be integrated in the digital platform and will be tracked by reporting method (app or web portal), who reported it (participant, proxy, or emergency contact), and who entered it (participant, proxy, or call centre). The digital platform will also include an investigator dashboard where investigators and selected study personnel can view and track, in real time, all AEs submitted. Role-based permissions will ensure only authorised personnel can view identifying confidential data like participant names.

The study app and web portal will be validated and compliant with good practice guidelines and regulations and the EU General Data Protection Regulation (GDPR). The app will support

iOS and Android operating systems. The app and web portal will be approved by local IECs and translated into local languages.

8.7.2 Study Call Centre

The call centre will be available to assist participants throughout the study, including during the informed consent and enrolment process. The call centre will operate in local languages. The call centre team will enter data into the digital platform on the participant's behalf. For consistency, the call centre will be provided with instructions on how to collect and enter data in a standardised way.

8.7.3 Record Retention

The study archive, including all source data, will be maintained for at least 5 years after the final report or first publication of study results, whichever comes later, in accordance with the International Society for Pharmacoepidemiology Guidelines on Good Pharmacoepidemiology Practices (GPP). Study records and data must be retained for longer than 5 years if required by applicable local regulations.

The Sponsor will comply with all the requirements of GPP and regional legislation related to archiving of study documentation. Records containing participant sensitive data will not be archived by the Sponsor, but must be kept with a CRO, investigators, and/or patient and according to local regulations pertaining to personal data protection.

Participant medical records must be kept for the maximum period permitted. Investigators and CRO personnel involved with handling participant medical records must agree to archive the documentation pertaining to the study after completion or discontinuation of the study, if not otherwise notified. They should not destroy any documents without prior permission from the Sponsor.

8.8 Data Analysis

This study is descriptive in nature. Proposed data analysis methods are summarised here. Detailed methodologies will be documented in a separate statistical analysis plan.

Sample Size. The planned sample size of this study is approximately 15,000 participants. For this study, the sample size reflects the Sponsor's best estimation of the enrolment potential in Germany, France, Spain, and Sweden, as well as the Sponsor's broader target to enrol between 30,000 to 40,000 participants across multiple studies. As described in the Vaccine COVID-19 Monitoring Readiness (ACCESS) protocol, a sample size of 30,000 with a mean follow-up of 12 months will be sufficient to rule out rare AEFIs with a frequency of more than 1:10,000 per person-year at an alpha of 5% (Meurs and Kant 2020). A sample size of 15,000 with 12 months follow-up would permit the frequency per year of common AEFIs to be estimated with a maximal confidence interval of $\pm 0.8\%$ using the binomial distribution. An

estimate of 12 months follow-up is used, rather than the full 18 months, to account for possible loss-to-follow-up.

Demographic and Baseline Characteristics. Distribution of participant characteristics at baseline will be described through point estimates (mean, median, rates, or proportions) and the corresponding variability (interquartile range, 95% confidence intervals). For a summary of participant demographics and characteristics to be collected at enrolment, refer to Table 3 in Section 8.4.1. Demographics and baseline characteristics collected in the participant enrolment questionnaire will also be used to categorise participants into subpopulations of interest (see Section 8.4.2) and to perform the subgroup analyses (described below).

Disposition. Participant dispositions will be tabulated, including study completion, study withdrawal, participants lost-to-follow-up, and deaths.

Primary and secondary analyses. The primary analysis will only include participants who enrolled within 7 days of vaccination with the first dose of AZD1222. All AEs collected, regardless of seriousness, will be tabulated. The cumulative incidence of SAEs, AESIs, and medically-attended AEFIs will be computed as the proportion of participants who reported an event among all AZD1222 vaccinated participants who completed each study-defined follow-up interval as well as among all AZD1222-vaccinated participants regardless of completion status, in combination with corresponding patient-years.

Where feasible, incidence rates will be calculated (in person-years), both by dividing by number of person-years, as well as by taking into account death as a competing event and withdrawal from the study/loss-to-follow-up as a censoring event (using cumulative incidence). Kaplan-Meier curves will be used for this analysis where appropriate.

Summaries of SAEs, AESIs, and medically-attended AEFIs by intensity, seriousness, and relatedness will also be presented.

In the pregnancy sub-cohort, the prevalence of pregnancies that resulted in live births, spontaneous abortions, and stillbirths will be summarised along with any other pregnancy outcomes reported within the AESI medical concept of Pregnancy Outcomes - Maternal. Infant outcome measures will also by summarised by the prevalence of events in the AESI medical concept of Pregnancy Outcomes – Neonates, including small for gestational age and major congenital malformations.

Additional Supportive Analysis. To support safety signal evaluation, a risk assessment will be conducted for AESIs using background event rates established through the ACCESS project or another source (Meurs and Kant 2020, ACCESS 2020). To further enhance background rate identification, additional literature review will be conducted if ACCESS data is insufficient or unavailable. Appropriate risk windows will be estimated for these analyses

and counts of AESIs that occurred within the prespecified risk window will be compared against expected values using sequential testing. Where appropriate, analyses will be stratified by sex and age. To assess whether larger risks can be found based on bias, the background rates based on the external sources will be evaluated as they are and with additional scenarios.

Subgroup Analyses. Incidence rates and potential differences in the risk and pattern of participants experiencing AEs within different subgroups will be explored, including categories that are considered missing information at the start of the study. The subgroup analyses will include:

- Age at vaccination (18 to 34, 35 to 49, 50 to 64, 65 to 79, and \geq 80 years)
- Sex (male, female)
- Race/ethnicity
- Country (Germany, France, Spain, Sweden)
- Previous COVID-19 infection
- Pregnant/breastfeeding women
- Participants with immunodeficiency
- Participants with autoimmune or inflammatory disorders
- Frail participants with comorbidities (chronic obstructive pulmonary disease, diabetes, chronic neurological disease, or cardiovascular disorders)
- Participants who receive other vaccines in addition to AZD1222 (within 1 month)
- Number of AZD1222 doses received (1 dose, 2 doses)

Handling of Missing Data. No restrictions on the percentage of missingness will be made, but the baseline characteristics of the participants lost-to-follow-up will be tabulated. The differences between the baseline characteristics for the total group and the group lost-to-follow-up will be related to the subgroup analyses to assess for a possible impact on AE risk. Adjustment for missingness will be further specified in the statistical analysis plan but may include multiple imputation, joint modelling, and inverse probability weighting.

To deal with missingness due to death, death will be interpreted as a competing risk in the above analyses.

Mitigation of Potential Bias and Confounding. Strategies include:

- To account for possible sampling bias due to the recruitment of vulnerable populations first (residual confounding), in the risk assessment analyses, in addition to the expected background event rate, the rates will be multiplied by 1.2, 1.5, and 2.0 times, for example.
- Subgroup analyses within risk assessment analyses will also be performed, if feasible. When characteristics are found that both are related to differences in AE risk and to differences between study participants and the overall vaccinated population, weighting will be added.
- Additional sensitivity analyses will include:
 - As participants can enrol in the study within 28 days of their initial vaccination, it will also be evaluated whether the AE risk for participants enrolling in the days and weeks after vaccination differs from the risk for participants enrolling immediately after vaccination. A sensitivity analysis will be performed that excludes subjects enrolled more than 2 days after the date of vaccination.
 - Participants who report pregnancy at the time of vaccination or an estimated date of conception within 45 days of vaccination will be included in the analyses for pregnant women. Sensitivity analyses will consider time windows less than 45 days.
 - Sensitivity analyses will evaluate the relationship between sex and loss-to-follow-up and the relationship between age and loss-to-follow-up.

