8.2 Study Design

This is a Phase IV real-world, observational, non-interventional, prospective cohort study of adults who receive the AZD1222 vaccine. Vaccine recipients \geq 18 years old will be recruited

for the study at vaccination sites in Germany, France, Spain, and Sweden. Awareness of the study may be raised through social media and traditional media (television, print, and radio).

In this study, vaccination sites will not act as traditional study investigators and will not be responsible for participant screening or safety follow-up. Rather, participants will self-enrol in the study using the study app, web portal, or call centre and will submit answers to study questionnaires using those methods. Event follow-up and assessment, where needed, will also be performed remotely by study personnel. The digital platform will also include an investigator dashboard where investigators and selected study personnel can view and track, in real time, all adverse events (AEs) submitted. Role-based permissions will ensure only authorised personnel can view identifying confidential data like participant names.

Participants will enrol in the study after vaccination with AZD1222. Enrolment is permitted within 28 days of the first dose of AZD1222 and can be completed at the vaccination site or remotely. If a vaccine recipient chooses to enrol in the study at the vaccination site, a study research coordinator may be present and can assist by:

• Providing information about the study.

SCI

- Explaining the study participation options: study app, web portal, or telephone communication with the call centre.
- Assisting the participant with the informed consent process.
- Checking if participants meet the eligibility criteria and providing vaccination details.
- Recording contact information for the participant, the emergency contact (in case of apparent loss to follow-up), and the participant's proxy, if needed.
- Providing the proxy with instructions on how to assist the participant with reporting.

For vaccine recipients who would prefer to enrol remotely at a later date, up to 28 days after the first vaccine dose, a study information brochure will be available that includes instructions to remotely enrol (including electronic informed consent completion, where permitted) and their vaccination details (if a vaccination card was not already provided).

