8.4.2.2 Pregnant Women

At enrolment, females aged < 50 years will be asked the date of their last menstrual period and if they are currently pregnant. Those who have not reported pregnancy, will be prompted for this information at each safety follow-up. Women who report pregnancy will be asked for their expected due date. Their estimated date of conception will be calculated, and those vaccinated (either first or second dose) between 45 days prior to the estimated date of conception and, any other point during pregnancy, will be included in the pregnant women subpopulation.

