10.2 Collection and Assessment Process for Adverse Events

Adverse events will be collected from the time of informed consent through 18 months post-first dose for participants. However, among pregnant women, follow-up will continue for 12 months after the birth of the child or until 24 months post-first dose of the last participant enrolled, whichever happens first.

Participants will receive timed notifications via push notification, email, or phone call asking for any new or worsening health issues that have resulted in consultation with a medical doctor, an emergency room visit or hospitalisation, or a significant or long-term disability or incapacitation.

Participants can also submit unprompted AE information at any time though the app, web portal, or call centre. All AEs collected during this study will be considered solicited AEs, regardless if they were prompted or unprompted.

If a participant indicates a new or worsened health problem, the participant will be asked additional questions about the issue, intensity, treatment, and outcome. Adverse events collected for this study, both prompted and unprompted, will focus on the events of interest for the study assessments and analyses: SAEs, AESIs, and medically-attended AEFIs, including COVID-19 infections. Should other AE types, however, be reported, these will also be collected and managed accordingly and presented in the study report.

All collected events will be immediately available to study personnel in the investigator dashboard, where new events will be flagged. Study personnel will then validate the cases, request medical records, and assess seriousness and causality with input from HCPs and the medical records (Figure 2).

Study personnel will confirm all collected AEs with the participant, the proxy, the emergency contact, and/or through the review of medical records. If the participant received care from an HCP aside from their primary care physician, study personnel will follow up to obtain contact information for that HCP to permit a medical record request. Follow-up for AESIs with the HCP will include the completion of a targeted safety questionnaire. The adjudication committee can be consulted for advice on whether any reported non-serious symptoms or events may be a suspected AESI and will also adjudicate select AESIs (Section 10.6).

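### Pregnancy outcomes are summarised as a simple prevalence that ignores gestational age at entry, which biases the final spontaneous abortion proportion downward by an amount set by the unstated exposure mix

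*Protocol*

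**What the plan says.** For maternal outcomes, Protocol section 8.8 (primary and secondary analyses) states that "the prevalence of pregnancies that resulted in live births, spontaneous abortions, and stillbirths will be summarised", together with other events in the maternal AESI concept. Infant outcomes are "summarised by the prevalence of events in the AESI medical concept of Pregnancy Outcomes – Neonates, including small for gestational age and major congenital malformations"; no denominator is named for them.

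Section 8.4.2.2 defines the sub-cohort as "those vaccinated (either first or second dose) between 45 days prior to the estimated date of conception and, any other point during pregnancy". Section 8.2 adds: "Enrolment is permitted within 28 days of the first dose of AZD1222". Section 10.2 sets the start of event capture: "Adverse events will be collected from the time of informed consent through 18 months post-first dose for participants".

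Three provisions in section 8.8 concern timing:
- The primary analysis is limited by enrolment delay: "The primary analysis will only include participants who enrolled within 7 days of vaccination with the first dose of AZD1222".
- A sensitivity analysis drops participants enrolled more than 2 days after vaccination.
- For pregnancy, "Sensitivity analyses will consider time windows less than 45 days".

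The eleven subgroup factors in section 8.8 do not include gestational age or trimester at exposure.

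**The concern.** A pregnancy contributes risk of an outcome only from the gestational age at which it comes under observation. A woman vaccinated and enrolled after the cut-off for spontaneous abortion cannot have one in the study. A woman enrolled at 37 weeks or later cannot have a preterm birth. A loss before consent falls outside formal event capture. In a simple prevalence of pregnancies, such women add to the denominator and cannot add to the numerator.

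Pregnancy and infant outcomes are two of the five secondary objectives (Table 2), and use in pregnancy is listed as missing information (section 6.2). Both pregnancy concepts are AESIs (Table 5). Section 8.8 plans to test AESI counts against external background rates, with stratification named only for sex and age. The bias scenarios there multiply the expected rates by 1.2, 1.5 and 2.0. If these were applied to spontaneous abortion, a diluted observed count would be set against a raised expected count, and both would push towards no signal.

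**Working it through.** The protocol gives no figure for pregnancy outcomes, so there is none to reproduce. Its ±0.8% precision (1.96 × √(0.25/15,000) = 0.0080) is for the whole study.

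**Inputs from the protocol.** Exposure runs from 45 days before conception to the end of pregnancy. With conception at gestational week 2, the window opens at 2 − 45/7 = −4.43 weeks. Closing it at week 40 gives 44.43 weeks. Enrolment lag is 0-7 days (primary analysis) or 0-28 days (all enrolled).

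**Assumptions, not in the protocol.** True spontaneous abortion risk is 10-20%, falling between weeks 5 and 20, with a hazard that is flat or declines more or less steeply. Preterm risk is 6-10%. Several exposure mixes are tried.

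**Spontaneous abortion, by hand.** Take risk 15%, flat hazard, uniform exposure and no lag. The hazard is h = −ln(0.85)/15 = 0.01083 per week. Per week of exposure time:
- Entry before week 5: 9.43 weeks, all intact. Later losses 9.43 × 0.15 = 1.41.
- Entry in weeks 5-20: intact at entry (1 − 0.85)/h = 13.84. Later losses 13.84 − 15 × 0.85 = 1.09.
- Entry in weeks 20-40: intact 20 × 0.85 = 17.00. Losses 0.

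Crude proportion = (1.41 + 1.09)/(9.43 + 13.84 + 17.00) = 2.51/40.27 = 6.2%, or 0.42 of the true 15%. The share entering at or after week 20 is 17.00/40.27 = 42%.

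If exposure stops at week 8, entry in weeks 5-8 gives 2.95 intact and 2.95 − 3 × 0.85 = 0.40 losses. The crude proportion is (1.41 + 0.40)/(9.43 + 2.95) = 14.7%, a ratio of 0.98.

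**Spontaneous abortion, by simulation** (400,000 conceptions per scenario; ratio of crude to true):

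| Exposure mix | Lag 0-7 days, risk 10-20% | Lag 0-28 days, risk 15% |
|---|---|---|
| Uniform over the protocol window | 0.26-0.42 | 0.25-0.38 |
| Already pregnant, weeks 4-40 | 0.07-0.26 | 0.05-0.21 |
| Week 14 onward only | 0.00-0.04 | 0.00-0.03 |
| Early only, to week 8 | 0.85-0.97 | 0.76-0.93 |

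**Does delayed entry repair it?** With risk 15%, declining hazard, uniform exposure and lag 0-7 days, the crude proportion is 4.7% (4.7/15 = 0.31). Restricting to entry before week 20 but staying crude gives 8.3%. A Kaplan-Meier estimate with delayed entry at enrolment gives 15.0%. It cannot recover risk that nobody was observed for: if all exposure is from week 14 on, it gives at most 6.5% when the true risk is 15%, which is a risk conditional on reaching entry.

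**Preterm birth.** Assume preterm deliveries average week 34 and other deliveries occur at week 40. A preterm pregnancy can be exposed for a share x = (34 + 4.43)/44.43 = 0.865 of the window. At 6% risk, crude = 0.06 × 0.865/(0.06 × 0.865 + 0.94) = 5.2%, a ratio of 0.87. For exposure in weeks 14-40, x = 20/26 = 0.769, crude 4.7%, ratio 0.78. Over 6-10% risk and the mixes tried, the ratio is 0.78-0.88.

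**Malformations.** Under uniform exposure, an assumed sensitive window of weeks 4-12 or 2-14 holds 8/44.43 = 18% or 12/44.43 = 27% of exposures. A true relative risk of 2 in that window, pooled over all exposure times, appears as 1 + 0.18 = 1.18 or 1 + 0.27 = 1.27.

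**The case against.** The strongest reply is that section 8.8 calls its methods proposed and leaves detail to a SAP, which is not shown here. Outcome-specific denominators and delayed entry could be set out there, and the study is descriptive. This stands in part: nothing in the protocol forbids a better analysis. But the protocol does more than stay silent. For other events it names person-years, competing death and censoring; for pregnancies it names a prevalence. Applied as written, that estimator is biased.

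Several stronger readings are tempting, and the documents do not support them:
- **The crude figure is only about 13% of the truth.** That follows if every woman enrols already pregnant, spread over weeks 4-39. Section 8.4.2.2 also admits women vaccinated before conception and women exposed by a second dose. Many of them would have enrolled before or early in pregnancy, with little or no left truncation.
- **All outcomes share one denominator.** The wording refers to pregnancies only for maternal outcomes; the infant denominator is not stated.
- **Timing is checked only by the shorter pre-conception window.** The 7-day restriction and the 2-day sensitivity analysis bear on losses between vaccination and enrolment. None of them addresses gestational age at entry.
- **Losses before enrolment are never seen.** Last menstrual period and obstetric history are collected at enrolment (Table 3), and records from the time of vaccination can be accessed (section 8.3.2.1). What can be said is that formal event collection starts at consent.
- **No comparison with background rates is possible.** Section 8.8 provides for risk windows, stratification where appropriate, and weighting. None of these is tied to gestational age.
- **The bias always runs downward.** In quarterly interim reports, a denominator of completed pregnancies would overstate spontaneous abortion, because losses end sooner than births.

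**Conclusion.** The point holds for the final analysis as described. A prevalence of pregnancies over a sub-cohort that enters at any gestational age understates spontaneous abortion. How far depends on the exposure mix, which the protocol does not give. Under assumed true risks of 10-20% and a lag of at most 7 days, the shortfall is about 58-74% for uniform exposure over the protocol window and about 3-15% for almost entirely early exposure. A 28-day lag takes the latter up to 24% at 15% risk. A general statement that the rate is grossly understated is therefore not warranted. Preterm dilution is modest, about 12-22%. Attenuation of a malformation effect is conditional on pooling all exposure times. The planned sensitivity analyses would not reveal any of this, because none varies gestational age at entry.

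**What to change.** State in the analysis section, and carry into the SAP, that gestational age is the time scale and that entry is the later of the qualifying vaccination and enrolment. Then, by outcome:
- **Spontaneous abortion:** cumulative incidence with delayed entry, among pregnancies entering before the case-definition cut-off.
- **Stillbirth:** pregnancies ongoing at that cut-off, with delayed entry for those who join later.
- **Preterm birth:** pregnancies exposed, enrolled and still ongoing before 37 weeks.
- **Major congenital malformations:** by trimester of exposure, with periconception and first-trimester exposure as the main denominator.
- **Small for gestational age:** live births.

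Report the distribution of gestational age at entry beside each estimate. If few women enter early, label the spontaneous abortion estimate as conditional on reaching the earliest well-populated week. Keep the crude proportions as supportive listings and do not compare them with background rates.

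Last menstrual period, due date and vaccination dates are already collected, and enrolment is dated by the study, so no new data are needed. The cost is a few sentences of text, smaller denominators and wider intervals. Delayed entry also assumes that women who enter later have the same subsequent risk as those already under observation at that gestational age; this should be stated.

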8.3.2 Study Population

8.3.2.1 Eligibility Criteria

Participants are eligible to be included in the study only if all the following criteria apply:

- Aged 18 or older at the time of vaccination.
- Received AZD1222 as the first dose of COVID-19 vaccination in the prior 28 days.
- The participant has provided sufficient details to validate the vaccination (vaccination card, batch/lot number, and/or regional vaccination register details).
- Provided informed consent to participate in the study, either personally or through a legal representative.
- Able and willing to provide responses to study notifications using the mobile device app, web portal, or call centre or have a proxy (a caregiver, family member, or other trusted individual) who can do so on their behalf.
- Able and willing to grant, personally or through a legal representative, permission to contact the participant's healthcare providers and to access the participant's medical records at the time of vaccination and during the post-vaccination follow-up period.

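### Section 8.8 names no analysis that separates follow-up after a different COVID-19 vaccine, and its dose-number subgroup places mixed-schedule participants in the single-dose category

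*Protocol*

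**What the plan says.** - **Eligibility (Protocol 8.3.2.1)** fixes the brand of the first dose only: "Received AZD1222 as the first dose of COVID-19 vaccination in the prior 28 days". Nothing excludes a later COVID-19 dose of another brand.
- **Event collection (Protocol 10.2)** has no stop at another vaccine: "Adverse events will be collected from the time of informed consent through 18 months post-first dose for participants". The first secondary objective (Table 2) covers the same 18 months after at least one AZD1222 dose.
- **Incidence (Protocol 8.8)** is computed in those who completed each follow-up interval and also "among all AZD1222-vaccinated participants regardless of completion status". For the time-based version, death is the only competing event named. Withdrawal and loss to follow-up are the only censoring events.
- **Subgroups (Protocol 8.8)** include "Participants who receive other vaccines in addition to AZD1222 (within 1 month") and "Number of AZD1222 doses received (1 dose, 2 doses").
- **Sensitivity analyses (Protocol 8.8)** deal with time to enrolment, the pregnancy window, and the relation of sex and age to loss to follow-up. None deals with a later COVID-19 vaccine.
- **Data collection (Protocol Table 3)** asks about recent non-AZD1222 vaccination at enrolment and at every safety contact to 18 months. The vaccination-details questionnaire lists brand and date. Second doses are expected between weeks 4 and 14.

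**The concern.** The objectives concern the safety of AZD1222, including over the long term. Protocol 6.2 lists both long-term safety and interactions with other vaccines as missing information, and 8.8 says the subgroups will cover such topics. Under the rules as written, a participant who has one AZD1222 dose and then another COVID-19 vaccine keeps contributing events and person-time to the same incidence for the rest of the 18 months.

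The 1-month subgroup does not isolate these participants. Someone with a single AZD1222 dose has only that dose to count the month from. With second doses expected at weeks 4 to 14, most later COVID-19 doses would fall outside the window. Those inside it would be mixed with, for example, influenza vaccinations.

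The dose-number subgroup is the more exposed result. Its lower category pools people who had one AZD1222 dose and nothing further with people who completed a course with another product. A difference between one and two doses could then not be read as an effect of dose number.

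**Working it through.** **Inputs from the protocol.** 15,000 participants; 18 months, shown as 78 weeks in Table 3; second dose expected at weeks 4 to 14; 14-week safety contact, taken here as the end of the primary period.

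**Assumed, because the protocol gives no figure.** Share *s* who receive another COVID-19 vaccine: 10%, 25% or 50%. Switch week *t*: 4 to 14. No other loss to follow-up.

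**1. The plan's own figures reproduce.** Section 8.8 says "A sample size of 15,000 with 12 months follow-up would permit the frequency per year of common AEFIs to be estimated with a maximal" half-width of 0.8%. Check: 1.96 × √(0.25/15,000) = 0.0080. The companion claim for 30,000 participants is to "rule out rare AEFIs with a frequency of more than 1:10,000 per person-year", "at an alpha of 5"%. With zero events the one-sided 95% upper limit is −ln(0.05)/30,000, or 1 in 10,014. Neither figure is in dispute. The point concerns which exposure the person-time belongs to.

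**2. Share of person-time after a switch.** Over 18 months: *s* × (78 − *t*)/78. Over the first 14 weeks: *s* × (14 − *t*)/14. For example, 0.10 × 64/78 = 8.2% and 0.50 × 74/78 = 47.4%.

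**3. Person-years left if censored at the switch.** 15,000 × [(1 − *s*) × 1.5 + *s* × *t*/52], against 15,000 × 1.5 = 22,500.

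| *s* | 18-month share after switch (week 14 to week 4) | 14-week share after switch | Person-years left (week 4 to week 14) |
|---|---|---|---|
| 10% | 8% to 9% | 0% to 7% | 20,365 to 20,654 |
| 25% | 21% to 24% | 0% to 18% | 17,163 to 17,885 |
| 50% | 41% to 47% | 0% to 36% | 11,827 to 13,269 |

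**4. Make-up of the single-dose category.** Mixed-schedule share = *s*/(*s* + *n*), where *n* is the share with no second dose of any kind. Assuming *n* = 10%:

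- *s* = 10%: 0.10/0.20 = 50%
- *s* = 25%: 0.25/0.35 = 71%
- *s* = 50%: 0.50/0.60 = 83%

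With *n* = 20% the shares are 33%, 56% and 71%.

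**5. Effect on the overall 18-month proportion.** Person-time after a switch is exposure, not bias, so a further assumption is needed. If the other vaccine adds an absolute 1% event risk among switchers, the proportion moves by *s* × 1%: 0.10, 0.25 or 0.50 points. All lie within the 0.8-point half-width. That half-width is the maximum, reached at a proportion of one half, so for rarer events the comparison is less reassuring.

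**The case against.** **It belongs in the SAP.** Section 8.8 defers detailed methods to a SAP that is not shown, and handling of later vaccines is often settled there. This stands in part: the SAP may already cover it. But the protocol itself fixes the denominators, the censoring events, the 1-month window and the two dose categories. A SAP that follows them without addition reproduces the gap.

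**Counting every later event is what the objective asks for.** This stands. The objective is incidence after at least one AZD1222 dose, and the study is descriptive. A reader might infer that the all-follow-up incidence is the wrong estimate; the objective does not support that.

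**Inclusion is not attribution.** This stands. A reader might infer that events after another product would be blamed on AZD1222. Protocol 10.1.5 provides a causality assessment for every SAE, AESI and medically-attended AEFI, and 8.8 summarises results by relatedness.

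**The AESI comparison with background rates is protected.** Largely so. Counts are limited to risk windows, so a broad effect there cannot be claimed. The windows' lengths are not given, so overlap with a later vaccine cannot be excluded either.

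**The dose label is literally correct, and subgroups are only explored.** True, but a correct count of AZD1222 doses still pools two different vaccination histories.

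**The size is assumption.** Also true. The protocol never mentions mixed schedules. Table 4 cites the availability of other vaccines only as an influence on recruitment and follow-up.

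**Conclusion.** The point holds in a limited form. Section 8.8 names no analysis that separates events and person-time after a non-AZD1222 COVID-19 vaccine, and its dose-number subgroup has no mixed-schedule category. A reader might go further and infer that the long-term results are contaminated. The documents do not support that, because they give no switching rate; the effect exists only to the extent that participants switch.

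The overall 18-month proportion may move little unless switching is common. The long-term picture of AZD1222 alone and the dose-number subgroup are the stronger grounds, since even 10% switching could make half of the single-dose category mixed-schedule when another 10% have no second dose. The 3-month primary result is exposed only for switches before its end. All sizes rest on the assumed switching shares, on timing at weeks 4 to 14, and on full follow-up.

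**What to change.** In Protocol 8.8 (and carried into the SAP):

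1. Keep the all-follow-up incidence as the estimate that matches the objective.
2. Add a supportive analysis of the 3-month and 18-month incidence with person-time split or censored at the first non-AZD1222 COVID-19 vaccine. Report events after that date separately beside it.
3. Apply the same split to any AESI risk window that extends past the switch.
4. Replace the dose-number subgroup by three groups: one AZD1222 dose only, two AZD1222 doses, and AZD1222 plus another COVID-19 vaccine. Treat exposure as time-varying, so that a participant contributes to each group only from the date of the relevant dose.
5. State which dose the 1-month window is counted from, and show COVID-19 vaccines apart from others in that subgroup.

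The cost is wording and one extra set of tables. No new contact is needed, because Table 3 already asks about non-AZD1222 vaccination at each safety contact. The sponsor should confirm that this item records product and date for every later COVID-19 dose.

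There are two drawbacks. The censored version has less person-time: at 50% switching, about 11,800 to 13,300 of 22,500 person-years remain. Censoring may also be informative if people switch because of an adverse event after the first dose. For both reasons it should be supportive only, with the post-switch events shown and not discarded.
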